7.3 Follow-up

7.3.1 VISIT 2 (~1 week post-dose 1± 1 day)

- Confirm ongoing consent prior to performing any study procedures. Conduct eligibility review. Review any AEs or SAEs that have occurred since the last visit as well as update the medical history and concomitant medications as necessary. Assess for injection site necrosis within 7 days of vaccination.
- Assess for urticaria, laryngospasm, bronchospasm, or anaphylaxis determined to be related to vaccine and within 7 days of vaccination.
- Assess for participants experience facial nerve neuropathy, confirmed by an investigator and determined to be related to vaccine.
 - Record oral temperature, pulse, and blood pressure
 - Targeted physical examination, if indicated based on review of medical history
 - Collect approximately 8 mL of venous blood:
 - 2 mL for serum ELISA and neutralization assays
 - 2 mL for ASC assay
 - 2 mL for ALS assay
 - 2 mL for ASC with homing
 - Collect plasma from PBMC tubes
- Collect stool (approximately 4 gm) and saliva (approximately 2 mL) for IgA assay.
- 1-2 gm of stool frozen at -80°C±15°C for future use microbiome studies
- Collect memory aid/reactogenicity information
- Provide stool sample collection container and instructions on how to collect stool sample
- Provide instructions to women participants to avoid pregnancy through the 28 days from receipt of the last dose of vaccine.
- Confirm date and time for Visit 3

7.3.2 VISIT 3 - Second Vaccination (~14 days post dose 1 ±2 days)

- This visit is ~14 days after the first dose for oral and SL cohorts and ~21 days after the first dose for the ID cohorts (window ± 2 days)
- Confirm ongoing consent and review eligibility criteria with the participant prior to performing any study procedures, to include updating the medical history and concomitant medications
- Record oral temperature, pulse, and blood pressure
- Targeted physical examination, if indicated based on review of medical history
- Collect approximately 6 mL of venous blood:
 - 2 mL for serum ELISA and neutralization assays
 - 2 mL for ASC assay
 - 2 mL for ALS assay
- Collect stool (approximately 4 gm) and saliva (approximately 2 mL)
- 1-2 gm of stool frozen at $-80^{\circ}\text{C} \pm 15^{\circ}\text{C}$ for future use microbiome studies
- Urine pregnancy test for all women will be performed and must be negative prior to dosing. Provide instructions to women participants to avoid pregnancy through the 28 days from receipt of the last dose of vaccine.
- Perform pre-vaccination reactogenicity assessment
- Administer vaccine dose 2, per the randomization code and observing the required pre-vaccination fasting for oral and rinsing for SL dosing
- Provide memory aid and other 7-day solicited AE and reactogenicity instructions
- Ask participant if they still have the digital thermometer for recording daily oral temperature for seven days following administration of the study product and offer re-instruction on the use of the thermometer as needed.
- Perform post-vaccination reactogenicity assessment after 90 minutes for oral cohorts and after 30 minutes for SL and ID cohorts. This assessment is to include unsolicited AEs and SAEs.
- Provide stool sample collection container and instructions on how to collect stool sample
- Confirm date and time for Visit 4

7.3.3 VISIT 4 (~1 week post-dose 2±1day)

- Confirm ongoing consent prior to performing any study procedures. Conduct eligibility review. Review any AEs or SAEs that have occurred since the last visit as well as update the medical history and concomitant medications as necessary
 - Assess for injection site necrosis within 7 days of vaccination.

- Assess for urticaria, laryngospasm, bronchospasm, or anaphylaxis determined to be related to vaccine and within 7 days of vaccination.
- Assess for participants experience facial nerve neuropathy, confirmed by an investigator and determined to be related to vaccine.
- Record oral temperature, pulse, and blood pressure
- Targeted physical examination, if indicated based on review of medical history
- Collect approximately 21mL of venous blood:
 - 2 mL for serum ELISA and neutralization assays
 - 2 mL for ASC assay
 - 2 mL for ALS assay
 - 2 mL for ASC with homing
 - 13mL for cryopreservation of PBMC, for memory B cell (5 mL) and effector T cell assays (8 mL)
 - Collect plasma from PBMC tubes
- Collect stool (approximately 4 gm) and saliva (approximately 2 mL) for IgA assay.
- 1-2 gm of stool frozen at $-80^{\circ}\text{C} \pm 15^{\circ}\text{C}$ for future use microbiome studies
- Collect memory aid/reactogenicity information
- Provide stool sample collection container and instructions on how to collect stool sample
- Provide instructions to women participants to avoid pregnancy through the 28 days from receipt of the last dose of vaccine.
- Confirm date and time for Visit 5

7.3.4 VISIT 5 - Third Vaccination (~14 days post dose-2 ± 2 days)

- This visit is ~14 days after the second dose for oral and SL cohorts and ~21 days after the second dose for the ID cohorts (window ± 2 days)
- Confirm ongoing consent and review eligibility criteria with the participant prior to performing any study procedures, to include updating the medical history and concomitant medications
- Record oral temperature, pulse, and blood pressure
- Targeted physical examination, if indicated based on review of medical history
- Collect approximately 6 mL of venous blood:
 - 2 mL for serum ELISA and neutralization assays
 - 2 mL for ASC assay
 - 2 mL for ALS assay
- Collect stool (approximately 4 gm) and saliva (approximately 2 mL) for IgA assay.

- 1-2 gm of stool frozen at $-80^{\circ}\text{C} \pm 15^{\circ}\text{C}$ for future use microbiome studies
- Urine pregnancy test for women will be performed and must be negative prior to dosing. Provide instructions to women participants to avoid pregnancy through the 28 days from receipt of the last dose of vaccine.
- Perform Pre-vaccination reactogenicity assessment
- Administer vaccine dose 3, per the randomization code and observing the required pre-vaccination fasting for oral and rinsing for SL dosing
- Provide memory aid and other 7-day solicited AE and reactogenicity instructions
- Ask participant if they still have the digital thermometer for recording daily oral temperature for seven days following administration of the study product and offer re-instruction on the use of the thermometer as needed.
- Perform post-vaccination reactogenicity assessment after 90 minutes for oral cohorts and after 30 minutes for SL and ID cohorts. This assessment is to include unsolicited AEs and SAEs.
- Provide stool sample collection container and instructions on how to collect stool sample
- Confirm date and time for Visit 6

7.3.5 VISIT 6 (~1 week post-dose 3 \pm 1 day)

- Confirm ongoing consent prior to performing any study procedures. Conduct eligibility review. Review any AEs or SAEs that have occurred since the last visit as well as update the medical history and concomitant medications as necessary
 - Assess for injection site necrosis within 7 days of vaccination.
 - Assess for urticaria, laryngospasm, bronchospasm, or anaphylaxis determined to be related to vaccine and within 7 days of vaccination.
 - Assess for participants experience facial nerve neuropathy, confirmed by an investigator and determined to be related to vaccine.
- Record oral temperature, pulse, and blood pressure
- Targeted physical examination, if indicated based on review of medical history
- Collect approximately 22 mL of venous blood:
 - 2 mL for clinical safety labs: ALT (also known as SGPT), total bilirubin, and creatinine
 - 2 mL for serum ELISA and neutralization assays
 - 2 mL for ASC assay
 - 2 mL for ALS assay
 - 2 mL for ASC with homing

- 12 mL for cryopreservation of PBMC, for memory B cell (5 mL) and effector T cell assays (7 mL)
- Collect plasma from PBMC tubes
- Collect stool (approximately 4 gm) and saliva (approximately 2 mL) for IgA assay.
- 1-2 gm of stool frozen at $-80^{\circ}\text{C} \pm 15^{\circ}\text{C}$ for future use microbiome studies
- Collect memory aid/reactogenicity information
- Provide stool sample collection container and instructions on how to collect stool sample
- Provide instructions to women participants to avoid pregnancy through the 28 days from receipt of the last dose of vaccine.
- Confirm date and time for Visit 7

7.3.6 VISIT 7 (~4 weeks post-dose 3 (window ± 3 days)

- Confirm ongoing consent prior to performing any study procedures. Conduct eligibility review. Review any AEs or SAEs that have occurred since the last visit as well as update the medical history and concomitant medications as necessary
 - Assess for injection site necrosis within 7 days of vaccination.
 - Assess for urticaria, laryngospasm, bronchospasm, or anaphylaxis determined to be related to vaccine and within 7 days of vaccination.
 - Assess for participants experience facial nerve neuropathy, confirmed by an investigator and determined to be related to vaccine.
- Record oral temperature, pulse, and blood pressure
- Targeted physical examination, if indicated based on review of medical history
- Collect approximately 17mL of venous blood:
 - 2 mL for clinical safety labs: CBC with differential for WBC, Hg, ANC, platelets; creatinine, albumin, and ALT
 - 3 mL for serum ELISA and neutralization assays
 - 12 mL for cryopreservation of PBMC, for memory B cell (5 mL) and effector T cell assays (7 mL)
 - Collect plasma from PBMC tubes
- Collect stool (approximately 4 gm) and saliva (approximately 2 mL) for IgA assay.
- 1-2 gm of stool frozen at $-80^{\circ}\text{C} \pm 15^{\circ}\text{C}$ for future use microbiome studies
- Provide stool sample collection container and instructions on how to collect stool sample
- Provide instructions to women participants to avoid pregnancy through the 28 days from receipt of the last dose of vaccine.
- Confirm date and time for Visit 8

7.3.7 **VISIT 8 (~12 weeks post-dose 3 (window ±1 week)**

- Confirm ongoing consent prior to performing any study procedures. Conduct eligibility review. Review any SAEs that have occurred since the last visit as well as update the medical history and concomitant medications as necessary, to support an SAE.
- Record oral temperature, pulse, and blood pressure
- Targeted physical examination, if indicated based on review of medical history
- Collect approximately 15 mL of venous blood:
 - 2 mL for serum ELISA and neutralization assays
 - 13 mL for cryopreservation of PBMC, for memory B cell (5 mL) and effector T cell assays (8 mL)
 - Collect plasma from PBMC tubes
- Confirm date and time for Visit 9

7.4 **Final Study Visit**

7.4.1 **VISIT 9 (~6 months post-dose 3, window ±2 weeks)**

- Confirm ongoing consent prior to performing any study procedures. Review any SAEs that have occurred since the last visit as well as update the medical history and concomitant medications as necessary, to support an SAE.
- Record oral temperature, pulse, and blood pressure
- Collect approximately 15 mL of venous blood:
 - 15 mL for cryopreservation of PBMC, for memory B cell (5 mL) and effector T cell assays (10mL)
 - Collect plasma from PBMC tubes

7.5 **Early Termination Visit**

Upon voluntary withdrawal of participation or any other reason for early termination from the study attempt to complete a clinic visit to include:

- Obtain an interim medical history and concomitant medication information and record on the appropriate case report form.
- Assess reactogenicity and review memory aid if early termination visit occurs within 7 days of any vaccination.
- Assess for unsolicited AEs if visit occurs within 28 days of third vaccination

- Assess for SAE during all early termination visits. Participants will be asked to be followed until resolution of any AEs.
- Record oral temperature, pulse, and blood pressure
- Perform a targeted physical examination, if indicated based on review of medical history
- Obtain serum samples for laboratory safety assays if visit occurs ≤ 28 days after third vaccination

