3.2 Study Outcome Measures

3.2.1 Primary Outcome Measures

The **Primary Safety Endpoints** to be used to evaluate reactogenicity, safety and tolerability are as follows:

- The occurrence of solicited local site and systemic reactogenicity events from vaccination through 7 days after each dose of vaccine is administered
- The occurrence of study withdrawals throughout the study
- The occurrence of discontinuation of study vaccination during the study

- The occurrence of unsolicited vaccine-related adverse events (AE), including laboratory AE, from first vaccination through 28 days after the last dose of vaccine is administered

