4 STUDY DESIGN

This is an outpatient Phase 1 double-blinded, placebo-controlled, dose-escalation trial in approximately 135 (plus any additional participants if needed to have minimal evaluable participants / cohort as described in [Table 1](#)) apparently healthy adult volunteers, age 18-45 years, who meet all the eligibility criteria and reside in Bangladesh, an endemic country for ETEC infection. The study population will be recruited from Mirpur, a densely populated urban slum community of Dhaka, Bangladesh, known as having a high rate of diarrheal, respiratory and enteric disease.

This clinical trial is designed to assess the safety, reactogenicity, tolerability, and immunogenicity of a range of dosages of dmLT administered by three different routes: oral, SL, or ID. The schematic of study design is presented in [Table 1](#). The oral and SL routes of administration will evaluate dosages of 5, 25, and 50 μ g of dmLT; the ID route of administration will evaluate dosages of 0.3, 1.0, and 2.0 μ g of dmLT. Participants will receive a total of three sequential doses of dmLT; the oral and SL routes will be at days 1, 15, and 29 and the ID route will be at days 1, 22, and 43. After each dose of study product, participants will be observed for 30-90 minutes, depending on the route of administration.

Safety, reactogenicity, and tolerability of the study products will be evaluated for each participant. Solicited local and systemic reactogenicity will be collected for 7 days after each vaccine administration. Memory Aids and digital thermometers will be given to participants to record solicited local and systemic reactogenicity including elevated body temperature (i.e., fever) at home, and they will be reviewed with the participants. Unsolicited AEs will be collected from the time of each study vaccination through 28 days after the last vaccination. Safety laboratories will be collected on Visit 7 or about 28 days after the last vaccination. Serious adverse events (SAEs) will be collected from the time of the first study vaccination through 6 months after the last study vaccination. Tolerability of the study products will be assessed by recording the occurrence of and reason for study withdrawals and discontinuation of study vaccination during the study.

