The evaluation of immunogenicity will include dmLT-specific antibody responses in serum, fecal, salivary and ALS samples, in addition levels of ASC in circulation will be determined. Memory B cells specific for dmLT will also be evaluated. An in-depth evaluation of effector and memory T cells response, including homing potential, cytokine/chemokine production profile, degranulation capacity, and activation potential, will also be performed. In order to maximize our ability to compare immune responses between US and Bangladesh studies, the timing of the sample collections for the immunological assays needs to be comparable. The timing of the specimen collection for the immunological assays were selected based on previous

DMID-funded dmLT studies conducted in the U.S. (i.e., DMID protocols 09-0066 and 12-0023) and the ongoing study 13-0013.

Additional participants may be enrolled to ensure there are at least 11 evaluable participants (10 vaccinees and 1 placebo) in each of the cohorts (cohorts A through I). Evaluable participants are defined as completing all 3 doses of vaccine and providing both safety and protocol-required specimens through at least 7 days after the third dose of vaccine. If additional participants are required, to maintain blinding, treatment assignments of additional participants are to be determined by Emmes.

The duration of the study for each participant will be up to 9 months (inclusive of the screening period through 6 months after the third dose of vaccine, plus a 2-week window on the last visit), depending on the route of dmLT administered. Details on the study procedures, evaluations, and study schedule are in [Sections 7, 8](#) and [Appendix A](#), respectively.

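### If Visit 7 is held early, no scheduled visit asks about non-serious adverse events starting up to day 28 after the last dose, and the diary can be collected before its Day 7 entry

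*Protocol*

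**What the plan says.** **Endpoints.** Protocol 3.2.1 ties two primary safety endpoints to fixed periods. The solicited one is "The occurrence of solicited local site and systemic reactogenicity events from vaccination through 7 days after each dose of vaccine is administered". The unsolicited one counts vaccine-related AEs, including laboratory AEs, "from first vaccination through 28 days after the last dose of vaccine is administered". Protocol 4 sets the matching collection rule: "Unsolicited AEs will be collected from the time of each study vaccination through 28 days after the last vaccination". SAP 4.5.1 places the end of that period at Day 57 for the oral and sublingual cohorts and Day 71 for the intradermal cohorts.

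**Visits.** Visit 7 (Protocol 7.3.6, "VISIT 7 (~4 weeks post-dose 3", ±3 days) reviews all AEs and SAEs since the previous visit. At Visit 8 (7.3.7) the instruction becomes "Review any SAEs that have occurred since the last visit", with history and medication updated only where they support an SAE. Visit 9 (7.4.1) is the same, and footnote 1 of Appendix A confirms it for both. Visits 2, 4 and 6 (7.3.1, 7.3.3, 7.3.5) fall one week after a dose, ±1 day, and each includes "Collect memory aid/reactogenicity information".

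**Evaluability.** Protocol 4 requires "completing all 3 doses of vaccine and providing both safety and protocol-required specimens through at least 7 days after the third dose of vaccine".

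**Analysis.** SAP 6.5 rules out imputation. SAP 9.3 uses the total population as the denominator for AE incidence. SAP 9.3.1 bases maximum severity on participants with non-missing data for the event. I found no rule for follow-up that stops before the endpoint period does.

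**The concern.** The endpoint periods end at 28 and 7 days, but the visits that close them may lawfully take place before those days. For the 28-day period, later visits do not fill the gap, because the question narrows to SAEs.

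At stake is the completeness of a primary safety endpoint in small cohorts. A participant seen early contributes no planned information on the last days but stays in the denominator, so any bias in the rate is downward. The same horizon appears in Protocol 9.5, where related facial nerve neuropathy within 28 days is a halting criterion: Visit 7 checks for it by name and Visit 8 does not.

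The diary issue is milder. What may be missing is the prospective Day 7 grade, and the tables that summarise over the week would not reveal it.

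**Working it through.** **1. The plan's nominal days (Appendix A).**
- Visit 7 minus dose 3: 57 − 29 = 28 (oral/SL); 71 − 43 = 28 (ID).
- Visit 6 minus dose 3: 36 − 29 = 7; 50 − 43 = 7.
- Visit 8 minus dose 3: 114 − 29 = 85; 128 − 43 = 85.

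The nominal schedule therefore matches both endpoint periods. Only the windows break the match.

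**2. Apply the windows.**
- Visit 7: 28 ± 3 gives post-dose days 25 to 31; the earliest is Study Day 54 (oral/SL) or 68 (ID).
- Visits 2, 4 and 6: 7 ± 1 gives post-dose days 6 to 8.
- Visit 8: 85 ± 7 gives post-dose days 78 to 92, SAEs only.

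**3. Size of the gap for a participant seen at the early edge.**
- Post-dose-3 period: days 26, 27 and 28, so 3/28 = 10.7%.
- Whole AE window from first vaccination: 3/(57 − 1) = 3/56 = 5.4% (oral/SL); 3/(71 − 1) = 3/70 = 4.3% (ID). This is the fairer share, because the endpoint starts at dose 1.
- Diary: 1/7 = 14.3% of the daily entries, or 1/8 = 12.5% of the 8 days that Protocol 11.4.2 summarises.

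**4. Averaged over participants.** The documents do not give the share seen early. With nobody early, the mean loss is 0 days; with everybody on day 25, it is 3 days. If attendance were uniform over the seven window days (an assumption), it would be (3 + 2 + 1)/7 = 0.86 days, and 0.86/28 = 3.1% of the post-dose-3 period.

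**5. Sensitivity to the anchor.** The section headings count from the dose, and I follow them. If the Appendix A windows were read from fixed study days and dose 3 were given 2 days late, the earliest visits would fall on post-dose day 54 − 31 = 23 and 35 − 31 = 4.

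**6. What one missed event means.** Protocol 11.2 gives an upper 95% bound of 30.8% for 0 of 10 vaccinees, and 1 − 0.025^(1/10) = 0.308 reproduces it. For 1 of 10, solving (1 − p)^10 + 10p(1 − p)^9 = 0.025 gives p = 0.445. One unrecorded event in ten would move the reported upper bound from 44.5% to 30.8%. This is an illustration; nothing in the documents shows that it happened.

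**7. Display of a missing Day 7.** The daily shells (SAP Table 113 and those in its format) carry a separate row for entries not reported. The any-event shells (Tables 97–104) and the maximum-severity shells (Tables 105–112) do not. A participant with entries for Days 1–6 only is classed there by those days, without a flag.

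**The case against.** The strongest reply is that much of the information has another route.

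- **Late AEs.** Protocol 7.6 allows non-serious AE review at an unscheduled visit within 28 days. Protocol 8.2.2 has staff follow up moderate or severe diarrhea within 28 days of any dose, at home if needed. Protocol 9.2.1 accepts AEs that surface when a participant seeks care or on monitor review. This stands as far as it goes, but each route depends on the participant coming forward or on chance. None is a scheduled question.
- **Day 7 events.** Appendix A marks AE review at Visits 3 and 5, and Visit 7 asks about everything since Visit 6. This stands. A reader might infer that Day 7 events are lost, but the documents do not support that.
- **Evaluability.** A reader might infer that a compliant day-6 Visit 6 makes a participant non-evaluable. Read literally it falls short at that moment, and hence possibly at the escalation review in Protocol 4.1. But anyone who then attends Visit 7 has supplied data and specimens beyond day 7. With 12 vaccinees enrolled and 10 required, three would have to fail before the minimum was missed, and extra enrolment is only permitted, not required.
- **Scope.** The endpoint counts only vaccine-related AEs, so unrelated late events leave it unchanged. Cohort E had no third dose and no Visits 6–9, and Cohorts F–I never enrolled (SAP 4.1 and 15).

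These replies narrow the point. They do not supply a planned question for days 26–28.

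**Conclusion.** The point holds in a limited form. A fully compliant schedule can leave up to 3 of the 28 days after the last dose without any planned question on non-serious AEs: 5.4% of the AE window for oral and sublingual participants and 4.3% for intradermal. Such participants still count in full in the denominator. Separately, the prospective Day 7 diary entry can be missing after each dose, and the any-event and maximum-severity tables do not show it.

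This rests on visit windows counted from the dose and on early visits actually having occurred, which the documents neither show nor exclude. A reader might also infer that early attendance differed between the sequential cohorts; nothing in the documents bears on that. Nor does the SAP hide every missing Day 7, since the daily tables show it.

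The point concerns ascertainment, is inexpensive to correct, and does not invalidate the safety analysis. For Cohort D, Visits 8 and 9 were not held, so an early Visit 7 there was the last scheduled contact.

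**What to change.** **Protocol**, for this design or any reuse of it:
- In 7.3.7 and Appendix A footnote 1, have Visit 8 also record non-serious AEs with onset through 28 days after the last dose. Keep the Visit 7 window. Moving it to 0/+6 days would close the gap too, but would put sampling as late as day 34, against the requirement in Protocol 4 that sample timing be comparable with the US studies.
- In 7.3.1, 7.3.3 and 7.3.5, when the visit precedes completion of the Day 7 entry, leave the memory aid with the participant or obtain that entry by phone.
- Reconcile the evaluability wording with the Visit 6 window.

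**SAP**, for data already collected:
- Beside the unsolicited-AE rates, give the number of participants in Cohorts A–D whose Visit 7 fell before post-dose day 28.
- Beside the any-event and maximum-severity solicited rates, give the number with no Day 7 entry, by dose. This count also applies to the two doses that Cohort E received.

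**Cost.** One short question at Visit 8 that relies on recall over several weeks, an occasional phone call, and two counts in the tables. The Visit 8 question could not have helped Cohort D, so the counts are the only remedy there. The laboratory part of the endpoint remains a draw that may fall on day 25.
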